Subject recruitment, enrollment, and interventions will be conducted in the adult intensive care units (Cardiac Care, Medical, Neuro, Surgical, and Specialty critical care) at University of Miami Hospital (UMH) and Jackson Memorial Hospital (JMH), both in Miami, Florida. UMH is licensed for 560 beds that includes 52 critical care beds. JMH is a 1,500 bed facility that includes 194 critical care beds and is the primary teaching hospital for the University of Miami Miller School of Medicine. Miami-Dade County is comprised of approximately 67.7% minority population. In our current and completed projects, we have established excellent research relationships and have been successful in meeting target enrollments in critical care. We will use mechanisms established in previous and current studies for providing staff in-services, unit meetings, and frequent communication about the study for nurses, physicians, and other ICU team members at UMH and JMH.

18. Resources Available

This 4-year R01 study is funded by National Institutes of Health, National Institute of Nursing Research. We have substantial experience, which enhances the likelihood that we can successfully accomplish the specific aims. We have conducted preliminary work to develop and refine important components of the project, including the intervention, study measures, and data analysis. We have completed a small RCT, which provided suggestive support for the proposed study's primary aim and informed decisions about the research plan. We have been active in funded research related to care of critically ill adults for over 2 decades, and have successfully conducted multiple RCTs in the critically ill population. We have direct and extensive experience

IRB Study Number: 20170771, Version #1.8, Date: 03/10/21, PI: [name]

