Delirium is an acute disturbance in attention (reduced ability to direct, focus, sustain, and shift attention) and awareness (reduced orientation to the environment), with additional change in cognition (memory, disorientation, or language disturbance).¹ Mechanically ventilated patients are especially at risk for cognitive dysfunction, and experience delirium at higher rates than patients who are not ventilated, with delirium occurring in as many as 80% of mechanically ventilated critically ill patients. It typically occurs within the first few days of intensive care unit (ICU) stay,² and results in significant negative outcomes.^{2,3} A recent meta-analysis of 16 studies involving 6,410 patients confirmed that delirium has direct negative effects on ICU and hospital length of stay and mortality.⁴ Number of days of delirium has been identified as an independent predictor of mortality in ICU patients.⁵⁻⁷ Meta-analyses have confirmed that patients with delirium have longer duration of mechanical ventilation, greater incidence of complications including nosocomial pneumonia and higher hospital mortality than patients without delirium.⁴

Sleep disturbances in the ICU have been associated with risk of delirium,^{3,8,9} and may also interact with interventions aimed at reducing delirium. A variety of other iatrogenic/environmental and biobehavioral factors (including environmental conditions, pharmacological therapies, disease severity and comorbid conditions, and demographic characteristics) are also theorized to affect the incidence of delirium.^{10,11} However, empirical evidence of the relationships of these factors to the development of delirium and its treatments is limited.

Importantly, delirium in the ICU not only complicates the hospital course, but is also associated with lasting sequelae.¹²⁻¹⁵ Data suggest that 25% to 78% of patients who have delirium in the ICU suffer clinically significant declines in cognitive function following their ICU stay.^{16,17}

IRB Study Number: 20170771, Version #1.8, Date: 03/10/21, PI: [name]

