Cognitive dysfunction may persist for months or be permanent,^{14,16,18} and is associated with impairments in daily function.¹⁹ In recent studies, increasing duration of delirium was an independent predictor of worse cognition 3 months and 12 months after ICU discharge,^{16,18} and this remained true even after adjusting for risk factors such as age, severity of illness, severe sepsis, and exposure to sedative medications in the ICU.¹⁶ Reducing delirium in mechanically ventilated ICU patients may reduce both short and long term cognitive dysfunction and posthospitalization disability.

To date, the focus of delirium research has been on detection of existing delirium and on its pharmacologic treatment.²⁰ In contrast, our approach focuses on prevention of delirium using a nonpharmacologic intervention.

Significance

Delirium is a common manifestation of cognitive dysfunction in critically ill patients, which is associated with substantial negative outcomes both during and following hospitalization. Using the published estimates²²⁻²⁴ that there are 5 million ICU admissions in the US each year, that approximately 40% of the critically ill require mechanical ventilation, and that delirium affects up to 80% of mechanically ventilated adult ICU patients, delirium likely affects an astonishing 1.6 million critically ill, mechanically ventilated ICU patients annually.

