The data obtained will provide empirical evidence that will enable us to evaluate the effect of the FAVoR intervention on delirium and holds promise to translate new knowledge into clinical decision-making about the management of delirium in the critically ill to ultimately improve patient outcomes, both in the ICU and as long-term survivors. We plan to publish the results of this study.

5. Inclusion and Exclusion Criteria

Since delirium in the ICU setting has a mean onset of 2.6 days (S.D.+/-1.7),⁴⁵ enrolling within 48 hours of initial intubation and ICU admission will initiate the FAVoR intervention prior to likely time of delirium onset. Male and female adults from all ethnic and racial backgrounds will be recruited.

For inclusion, mechanically ventilated subjects must be:

- at least 18 years old,

IRB Study Number: 20170771, Version #1.8, Date: 03/10/21, PI: [name]

- within 48 hours of initial intubation and ICU admission,
- they or their legally authorized representative (LAR) must be able to provide informed consent in English or Spanish, and
- a family member able to speak English or Spanish must be available and willing to audio record scripted messages.

Exclusion criteria include:

- dementia (because it complicates planned longitudinal cognitive assessments),
- anticipation by the clinical provider of imminent patient death,
- medical contraindication to the intervention (for example, psychiatric history of auditory hallucinations, or profoundly deaf), and
- inability to speak either English or Spanish.

We will use the procedure described by our consultant, [name], and his colleagues⁴⁵ to screen for pre-existing dementia as follows. The modified Blessed Dementia Rating scale (mBDRS)⁴⁷ will be used to screen for dementia using family interviews; it is a valid measure in ICU patients where direct patient assessment is not feasible.⁴⁸ Similar to Ely et al.,⁴⁵ we will include an additional family/surrogate question asking them to rate on a 5-point scale whether they believe the patient has dementia. We will also increase the sensitivity for detecting pre-existing dementia by excluding potential subjects with suspected dementia if they meet any of the following 3 criteria: (1) history of an expert diagnosis of dementia, (2) modified Blessed Dementia Rating scale score of at least 3, or (3) rating by the surrogate of at least 3 out of 5 as possibly having dementia.

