Because the intervention scripts have been developed, IRB approved, and pilot tested in English and Spanish, patients who do not speak either English or Spanish, as identified by self or their family, will be excluded.

Inclusion of Adults Unable to Consent

In our experience in conducting clinical research in the critical care areas, we have found that potential subjects who are mechanically ventilated are generally sedated to some degree. In addition, since use of mechanical ventilation primarily occurs during periods of patient instability, the use of sedation at these times is extensive and compromises patient's ability to communicate effectively which is compounded by the presence of the endotracheal tube. As a result, we have always found it appropriate to contact the legally authorized representative for consent. However, there may be rare occurrences when potential subjects are adequately oriented and lucid to be able to provide informed consent. Therefore, we will use the 2-step procedure described by Fan et al.⁷⁶ to determine the patient's ability to provide informed consent. Step 1 is objective evaluation with the Richmond Agitation-Sedation Scale (RASS) and the Confusion Assessment Method for Intensive Care Unit (CAM-ICU). Patients who score -1, 0, +1 on the RASS indicating drowsy, alert, or restless respectively and are not delirious (CAM-ICU = No) will move to Step 2. Step 2 is assessment for competency using the MacArthur Competence Assessment Tool for Clinical Research: MacCAT-CR that evaluates all four capacity domains for consent (understanding, appreciation, reasoning, expression of a choice). Evaluation of Step 1 requires approximately 2-3 minutes, Step 2 requires approximately 15 minutes. Fan et al.⁷⁶ found in consent evaluations of 150 ICU patients that 89% were sedated/delirious, and unable to provide consent; our experience in previous research is similar. Therefore, we expect that few potential subjects will move to Step 2 while critically ill and mechanically ventilated. The LAR will be contacted for those who fail Step 1 or Step 2.

IRB Study Number: 20170771, Version #1.8, Date: 03/10/21, PI: [name]

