Each message indicates that it is daytime (to provide general time orientation), states that the message is a recorded message, and tells the subject that he/she will hear messages frequently throughout the day to help him/her understand that he/she is in the ICU. Other than the patient's name, the recorded message is generic in nature, and not specific to any one patient condition, procedure, or family situation. Topics for message scripts were developed in response to patients' recollections of the ICU experience.³⁸⁻⁴⁰ The 8 recorded messages will vary randomly in order each day, reducing message repetition, which may eventually annoy or be ignored by the subject.

The messages will be recorded by a family member of the family's choice using a standardized script, in either English or Spanish, based on the family member's decision regarding which language would be most meaningful to the subject. Family members are not human subjects in this project; no data will be collected about the family members. The messages will be digitally recorded using audacity software and stored on the study computer's hard drive as a standard Microsoft wave files. The wave files are loaded onto a small, wireless, digital audio player with a wireless speaker, protected inside a disposable plastic bag, placed near the subject's ear, and set to shuffle play. Shuffle play is a mode of audio playback in which messages are played in a randomized order that is decided upon for all tracks at once and prevents repeated tracks, which makes it distinct from random playback. Shuffle play randomly selects the order of the messages to be played in the patient's room every hour for 8 hours during the daytime, beginning at 9:00 am. The digitally recorded messages will continue at the predetermined daytime intervals each day for a total of 5 days (120 hours), or until ICU discharge if ICU discharge occurs prior to 5 days. All intervention "doses" will be administered during the hours of 9:00 am and 4:00 pm for each of the 5 days, with intervention beginning at the earliest available time following completion of family recording. The research personnel will document the time and number of recordings each day so that a message "dose" can be documented. Research personnel will monitor the subject and the recorded messages regularly to document if the subject was not in the unit (for procedures off the unit etc.) so that those off-unit times can be included in the dose calculation.

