Inpatient. Once consent is obtained and the subject is enrolled, baseline data will be collected from medical records. In randomized assignment to the intervention group, the family member selected by the family to record scripted FAVoR messages will be contacted, and taken to a quiet area to complete the recording on the assigned computer. FAVoR will be delivered through a wireless speaker, which will be placed near the patient's head. Delivery of the intervention to subjects randomized to receive it will begin as soon as possible during 9 am and 4 pm; if the FAVoR messages cannot be recorded before 4 pm, the intervention will begin on the following morning at 9 am. Data recording devices (SP-PSG and ActiWatch) will be applied to the subjects receiving the intervention immediately prior to the onset of the FAVoR intervention, and to control subjects as soon as feasible following consent. Actigraphy and SPPSG will continue throughout the 120-hour period beginning with the intervention delivery and continuing until the same time 5 days (120 hours) later. Data collection will resume and continue after at least 24 hours of ICU discharge. The subject will complete the NIH Toolbox-Cognition Battery, and the PROMIS Global Health instrument, and actigraphy and SP-PSG will be obtained.

We will follow University of Miami Hospital and Jackson Memorial Hospital infection control policies and procedures for cleaning portable equipment before and between patients, which include appropriate germicidal or bleach agents and single use disposable equipment covers.

As of June 2020, we will resume data collection at UMH for the following measures: CAM-ICU, Actigraphy, SP-PSG, and the NIH Toolbox Cognition Battery. Data collection remains paused for these measures at JMH.

Outpatient. There will be two outpatient data collection events at 1 month and 6 months posthospital discharge. During the 1 month home visit, research staff will travel to the subject's home (or other location agreed upon) to administer the NIH Toolbox-Cognition Battery testing and the PROMIS Global Health assessment, PROMIS-SD, PROMIS-SRI, PROMIS-CF, PROMIS-CFA questionnaires. While face-to-face interaction is not permitted, the subjects will not be asked to wear the SP-PSG and ActiWatch (for acquisition of sleep and activity data) overnight. Identical data collection processes will be used at the 6 month visit.

Procedures for telephone or video conference:

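### About a third of delirium cases could begin before the latest permitted enrolment, yet admission CAM-ICU status reaches the primary analysis only if the arms look unbalanced

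*Combined protocol and SAP*

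**What the plan says.** **Timing.** Section 5 (Inclusion and Exclusion Criteria) states that "delirium in the ICU setting has a mean onset of 2.6 days (S.D.+/-1.7") and requires subjects to be "within 48 hours of initial intubation and ICU admission". It concludes that this "will initiate the FAVoR intervention prior to likely time of delirium onset".

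The 48-hour limit applies to enrolment, not to the first message. Section 9 (Description of Intervention) has delivery start "with intervention beginning at the earliest available time following completion of family recording". Its Inpatient paragraph adds: "if the FAVoR messages cannot be recorded before 4 pm, the intervention will begin on the following morning at 9 am". No maximum interval from enrolment to first message is given.

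**Delirium at entry.** It is not among the exclusions in Section 5. In the two-step consent procedure, a positive CAM-ICU moves the decision to the legally authorized representative and does not exclude the patient.

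**Data collected.** Table 1 (Section 7) marks CAM-ICU at Study Admission, on ICU Days 1-5 and on ICU Days 6-7.

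**Analysis.** Section 9 names no stratification factor for the permuted blocks. Part I of the Data Analysis Plan (Section 10) tests the primary hypothesis with an unadjusted chi-square test on a 2x2 table. It moves to logistic regression only for covariates found to differ between the arms. Admission CAM-ICU is not named there, and no threshold for imbalance is given.

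**The concern.** A mean of 2.6 days with an SD of 1.7 days leaves a good deal of onset before day 2, and the first message can come later than enrolment. Some subjects will therefore be delirious before they hear anything. Under Section 9 a day with any delirium is not delirium free, so delirium present at entry can count directly against the primary outcome in either arm.

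Admission status is therefore likely to be one of the stronger predictors of the outcome. With no stratification and no prespecified adjustment, a chance difference between arms shifts the estimate. Whether that shift is corrected depends on a look at the data. The plan also has no analysis restricted to subjects not yet delirious, although the Background says "our approach focuses on prevention of delirium using a nonpharmacologic intervention".

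**Working it through.** **Inputs from the documents.** Onset mean 2.6 days, SD 1.7 (Section 5). Latest enrolment 48 h = 2.0 days (Section 5). Overnight wait from 4 pm to 9 am = 17 h (Section 9). Delirium frequency: "delirium occurring in as many as 80% of mechanically ventilated critically ill patients" (Section 4), used as an upper figure. N = 182, 91 per group (Section 8).

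**Assumptions.** Onset is counted from ICU admission or intubation. The shape of its distribution is unknown, so several are tried. Onset is independent of enrolment time. No allowance is made for delirium that resolves before enrolment.

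The plan gives no share of subjects with onset before the first message, so there is no figure of its own to reproduce.

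**Step 1: start at the enrolment limit.** z = (2.0 - 2.6)/1.7 = -0.35, and Phi(-0.35) = 0.36.

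**Step 2: start after an overnight wait.** 48 + 17 = 65 h = 2.71 days. z = (2.71 - 2.6)/1.7 = 0.06, and Phi(0.06) = 0.53 (0.525 unrounded).

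**Step 3: vary the shape.** The lognormal, gamma and Weibull match the mean and SD. The truncated normal keeps the parameters 2.6 and 1.7. The last column averages P(onset < t) over t uniform on 0-48 h with no delay.

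| Shape | before 48 h | before 65 h | even 0-48 h |
|---|---|---|---|
| Normal | 0.362 | 0.525 | 0.187 |
| Normal cut at 0 | 0.319 | 0.493 | 0.132 |
| Lognormal | 0.444 | 0.643 | 0.144 |
| Gamma | 0.436 | 0.611 | 0.173 |
| Weibull | 0.430 | 0.594 | 0.186 |

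These are shares of delirium cases, not of subjects.

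**Step 4: convert to subjects at the 80% upper figure.**
- Even enrolment over 0-48 h, no delay: 0.8 x 0.132 to 0.8 x 0.187 = 11-15%, about 19-27 of 182.
- Even enrolment over 24-48 h, no delay: 21-30% of cases, about 31-44 of 182.
- All starting at 48 h: 0.8 x 0.319 to 0.8 x 0.444 = 26-36%, about 46-65 of 182.
- All starting at 65 h (extreme): about 72-94 of 182.

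**Step 5: room for chance imbalance.** With 91 per arm and a share p positive at admission, the SD of the between-arm difference is sqrt(2p(1-p)/91).
- p = 0.11: sqrt(2 x 0.11 x 0.89/91) = 0.046.
- p = 0.42 (normal shape, all starting at 65 h): sqrt(2 x 0.42 x 0.58/91) = 0.073.

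If imbalance were declared at two-sided p < 0.05 (an assumption), differences up to about 1.96 x 0.046 = 9 points, or 1.96 x 0.073 = 14 points, would usually go unadjusted. An imbalance of delta shifts the difference in outcome proportions by about delta x d, where d is the outcome gap between admission-positive and admission-negative subjects. The documents give no value for d.

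**The case against.** **The Section 5 sentence says likely, not certain.** 48 hours is before the 2.6-day mean, and under every shape tried 56-68% of onsets fall later. A reader might infer that the claim fails on the plan's own figures. It does not. It holds for most cases at the latest permitted enrolment and fails only for starts near or beyond 2.6 days.

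**The 65-hour start is an extreme.** It needs enrolment at the limit and a recording that misses 4 pm. Section 20 also allows recording by phone or Zoom. This stands, and it is why the even-enrolment figure of 13-19% belongs beside the others. Against it, Section 20 describes reaching family at the bedside within 48 hours as a particular difficulty, which points towards later starts.

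**The consent figure is weak evidence.** Section 5 reports that "89% were sedated/delirious, and unable to provide consent; our experience in previous research is similar". A reader might infer that most subjects are delirious at entry. The figure combines sedation with delirium and gives no delirium share. It shows only that many admission assessments may not be possible.

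**The primary hypothesis is not confined to new delirium.** Section 3 hypothesises less delirium, and Section 9 says the five days cover both the time before onset and the time when delirium is most frequent. Subjects delirious at entry can still gain delirium-free days if episodes shorten, so they inform the test. This stands. A reader might infer that the trial cannot answer its question. What is missing is only a supportive analysis that matches the prevention wording.

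**The imbalance rule could bring admission CAM-ICU in.** It could, so the plan does not ignore the variable. But with no threshold and no named covariate, the primary model would be chosen after seeing the data, and moderate imbalances would usually go unadjusted.

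**Conclusion.** The point holds as a gap in prespecification. About one third of delirium cases (32-44%) would begin before the 48-hour enrolment limit. About half (49-64%) would begin before a first message at 65 hours, and 13-19% under even enrolment with no delay. The last figure is about 11-15% of subjects, and it would be lower if fewer than 80% become delirious. All these figures rest on the assumed time origin, shape and enrolment pattern. The mean duration of 3.4 days cited in Section 9 suggests that most such episodes would still be present at the start.

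Even the low end is enough to make admission status worth handling by rule. The consequence is lost precision and sensitivity to chance imbalance. A reader might infer a biased comparison, but the documents do not support that, because randomisation protects it from systematic bias.

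**What to change.** Leave the enrolment window and delivery schedule as they are.

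1. **Data Analysis Plan, Part I.** Make the logistic regression already described there the primary analysis. Always include CAM-ICU status in three categories (negative, positive, not assessable), whatever the observed balance. Use the value recorded before randomisation or, failing that, before the first message, with the same timing rule for controls. Keep the unadjusted chi-square test as a supporting analysis.
2. **Supportive analysis.** Add an analysis, labelled as supportive, of new delirium in subjects who are CAM-ICU negative at admission.
3. **Section 5.** Say that most, but not all, subjects are expected to start before onset.

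**Cost.** The data are already scheduled for collection, so this is analysis-plan wording. It does replace the default primary test, and the odds ratio becomes conditional on admission status. The logistic model needs the binary outcome implied by the 2x2 table, so the cut on delirium-free days has to be stated. The admission-negative subset is smaller than the full sample. If many subjects are not assessable because of sedation, it shrinks further and the covariate gains less.
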